A total of 10 patients will be enrolled in the intervention (V-AD) arm of the study. These patients will be recruited from those presenting to Mayo Clinic Florida or Mayo Clinic Rochester with thoracic infections that require surgical intervention. A historic control group of 10 patients with open chest wounds who were treated with the traditional treatment techniques at Mayo Clinic will be selected using propensity-matching methods. We plan to complete our target accrual over a timeframe of approximately 12 months.

D.2. Subject Population

Subjects will be identified by the Principal Investigator or the Co-Investigators. Patients referred for surgical management of thoracic infections, who meet inclusion criteria and none of the exclusion criteria, will be invited to participate in the study. If the subject is interested in more information about

the study, a study coordinator will meet with the patient to discuss further and obtain informed consent.

D.3. Inclusion criteria

- 1. Subject provides informed consent and is:
 - a. >18 years of age,
- 2. Subject is scheduled to undergo surgical intervention(s) as part of the standard care for management of intrathoracic infection.

D.4. Exclusion criteria:

- D.4.1. Patients who have the following conditions will be excluded from participating:
 - 1. Patent bronchopleural fistulas.
 - 2. Severe respiratory failure requiring mechanical ventilation at the time of first consultation.
 - 3. Inability to provide informed consent due to physical or mental impairment.
 - 4. Altered mental status.
 - 5. Proven or suspected malignancy in the wound.
 - 6. Coagulopathy due to medical or pharmacologic reasons.
 - 7. Dependency on anticoagulants or antiplatelet medication due to high risk for adverse events if these medications are stopped for a prolonged period of time.
 - 8. Allergy to acrylic products.
 - 9. Subject is a pregnanat or lactating female

D.4.2. Patients in whom the use of V-AD is determined to be unsafe by the surgeon for any reason will be excluded from the study.

D.5. INITIAL EVALUATION AND INFORMED CONSENT FOR ENROLLMENT

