There are 2 types of foam dressings that will be used in the study:

- 1. An open pore reticulated polyurethane foam (V.A.C Granufoam Dressing)
- 2. A polyvinyl alcohol foam (V.A.C WhiteFoam Dressing).

The canister system is self-monitoring and can be set to different therapy modes (continuous or intermittent) depending on the individual patient and wound needs. In-built alarm systems can detect a loss of pressure or tubing blockage, alerting the care team to troubleshoot these issues.

G. DATA ANALYSIS

Exploratory analysis will be used to analyze the correlative studies comparing the healing rates. The analysis will include all 10 patients treated with V-AD and a matched group of 10 patients previously treated for empyema at Mayo Clinic. Due to the limited sample size the analysis will be descriptive and hypothesis generating. Any information that shows promise based on the pilot data will be explored in follow-up studies. Descriptive statistics, and scatter plots with 95% confidence intervals will graphed over time. Data will be visually inspected for differences.

The following datasets will be compared during analysis:

1. V-AD treated patients versus historical controls.

H. RISKS

H.1. Potential risks: The specific risks of V-AD use in the chest cavity have been reported and include pain, hypotension and difficulty in removing the sponge (11). No serious adverse events have been reported to date. General risks of NPWT when applied to other parts of the body include suction injury to skin and injury to underlying organs such as bowel or blood vessels. Extrapolating these adverse effects to the chest, there is an unquantifiable risk of injury to intrathoracic organs – lungs, heart, large vessels (aorta, pulmonary artery or veins). Hypothetically, injury to the lungs can lead to worsening of bronchopleural fistulas, air leaks or pulmonary hemorrhage; injury to the vascular structures can lead to significant hemorrhage, and even death. During removal of the black foam sponge dressing, it is possible to cause injury to the underlying structures due to excessive traction or adherence from tissue ingrowth.

H 1.1. Potential Severe Adverse Events

- Death
- Respiratory failure requiring ventilation (for any cause)
- Major cardiac arrhythmias requiring cardioversion or hospitalization which are hemodynamically significant.
- Massive Hemoptysis (life-threatening or requiring an intervention e.g. embolization)

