- Intra-parenchymal/intrapleural hemorrhage leading to hemodynamic instability or requiring any intervention to specifically address the bleeding.
- All new onset bronchopleural fistulas will be reported as SAE's.
- Worsening of pleural space infection requiring treatment with IV antibiotics, with exceptions as below:
 - Treatment of pathogens identified on microbiology obtained during the initial culture will not count as a new infection.
 - Requirement for sharp debridement of necrotic tissue or exudates identified during dressing changes will not be considered an adverse event, as this is normal during management of infected wounds.

H.1.2. Other Adverse Events

- Minor cardiac arrhythmias NOT requiring cardioversion, hospitalization and/or are NOT hemodynamically significant.
- Minor Hemoptysis or minor intra-parenchymal/intrapleural hemorrhage
- Pneumonia/pleural space infection treated as outpatient
- Mild (<4/10, not requiring IV medication) to moderate pain (requiring IV medication or rated as >5/10)
- DVT or Pulmonary Embolus treated with anticoagulation alone

H.2. Risk Prevention and Monitoring: In order to decrease the risks of these potential adverse events, the following safety precautions will be taken:

- 1. The dressings will not be applied directly in contact over any exposed blood vessels, heart or lung, or anastomotic sites.
- 2. Mepitel[®] (Mölnlycke Health Care, Norcross, GA), a silicone-based perforated non-adherent dressing will be placed over any delicate organs such as the heart or the lung. This will prevent adherence of the foam dressing to the underlying tissue while allowing drainage. Mepitel[®] itself can be easily removed as it is non-adherent.
- 3. The black foam dressing will not be used directly over any organ/structure likely to be traumatized during removal of the dressing. Instead, the white foam will be used as the first layer. The black foam may be placed over the white foam in such instances.
- 4. Prior to removal, the dressings will be thoroughly soaked with normal (0.9%) saline to disengage the dressings easily.

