- 5. The number of individual pieces of foam dressing placed during each dressing change will be documented and care will be taken to ensure that the same number of dressings is removed (and documented). In case there is a discrepancy in the tally of foam pieces placed and removed in consecutive dressing changes, the surgeon will be contacted immediately. V-AD will not be reapplied until the surgeon confirms that no foam piece has been retained in the wound by personally examining the wound.

We plan to monitor and report all of the above adverse events from the first application of the V-AD to one week after final closure of the wound or termination of V-AD therapy. All standard precautions will be taken to minimize risk. Patients will be monitored in a telemetry unit during hospital admission for complications including bleeding, hemodynamic instability (heart rate < 60 or > 120, systolic BP <90 or > 150, diastolic BP < 50 or > 100, respiratory compromise (SpO2 < 92% on room air).

All data regarding risk/adverse events will be collected in person while the patient is admitted to the hospital or seen in clinic or over the telephone if the patient is outpatient.

The primary endpoint of this study is efficacy of treatment. However, safety is also a critical component and will be defined by the rate of severe adverse events (see below). In addition to major complications, all intermediate and minor complications will also be recorded.

H.3. Evaluation and Grading of Adverse Events

H.3.1. Performing Adverse Events Assessments

The Principal Investigator will be responsible for promptly documenting and reporting all adverse events (AEs) observed during the study. If the AE is considered severe, the investigator must report the AE immediately to the DSMB through Mayo Clinic Rochester. All AEs considered "severe" will be reported no later than 24 hours after the investigator recognizes/classifies the event as a severe adverse event.

For all SAE's, the study will be placed on hold until the DSMB has reviewed and notification received to continue study accrual. The safety monitoring board may require study protocol modifications or cessation of all study activities prematurely.

H.3.2. Adverse Event Definitions

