The following definitions of terms are guided by the International Conference on Harmonization, the U.S. Code of Federal Regulations [21 CFR 312.32] and European Union Directive 2001/83/EC and are included herein. An adverse event will be defined as any unexpected medical event associated with the use of the procedure in a human subject, whether or not considered directly procedure-related. An adverse event can be any unexpected or abnormal clinical sign or condition temporally associated with the procedure.

H.3.3. Severity of Adverse Events

Adverse events are graded based on the National Cancer Institute (NCI) Common Terminology Criteria for Adverse Events (CTCAE) version 4.0.

H.3.4. Communicating Severe Adverse Events

The principal investigator accepts all responsibilities for AE identification, documentation, grading, and prompt notification of the safety monitoring board no later than 24 hours after the occurrence of the event. The board will then have 24 hours to review the provided data, determine the appropriate course of action including possible modification of the existing protocol, temporary study hold or study cessation.

I. BENEFITS

There is no guarantee that the subjects will receive any benefit from this study. The research team hopes that the use of V-AD will lead to faster closure of the open chest wound by eliminating infection and promoting granulation tissue, but this remains hypothetical.

J. PAYMENT AND REMUNERATION

Subjects will not be paid to participate in the study.

K. COSTS

There will be no additional costs to subjects for participating in this study. Subjects and/or their insurance companies will be responsible for all care provided as part of the wound care with V-AD as this service is part of the standard of care they would receive for their condition.

Any costs related to laboratory analysis that is not considered standard of care, will be covered by the investigator group.

L. RESOURCES TSFRE grant \$25,000

Reference:

1. Al-Mufarrej F, et al. Outpatient management of post-pneumonectomy and post-lobectomy empyema using the vacuum-assisted closure system. *Surgery Today*. 2010 Aug;40(8):711-8.

2. Badreldin AM, et al. Successful management of a massive residual space empyema using intrathoracic vacuum-assisted instillation. *Thoracic and Cardiovascular Surgery*. 2013 Oct;61(7):642-5.

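### The safety endpoint, the 24-hour report and the study hold all depend on what counts as a severe adverse event, but the protocol's rules conflict, so device harms it foresees may go uncounted

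*Combined protocol and SAP*

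**What the plan says.** Efficacy is the primary endpoint. On safety, H.2 adds that "safety is also a critical component and will be defined by the rate of severe adverse events (see below". The text below that sentence is H.3. H.3.1 makes the investigator report any event regarded as severe to the DSMB within 24 hours, and puts the study on hold for every SAE until the board has reviewed it. H.3.3 grades events by CTCAE v4.0. H.3.2 says "An adverse event will be defined as any unexpected medical event associated with the use of the procedure in a human subject".

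The itemised list stands above, under the heading "H 1.1. Potential Severe Adverse Events". It names death, respiratory failure needing ventilation, major arrhythmia, massive hemoptysis, hemorrhage, new bronchopleural fistula and worsening pleural infection. H.1.2 lists other adverse events. H.2 ties the planned monitoring to the events listed above it.

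The protocol foresees further harms from the dressing. H.1 says "The specific risks of V-AD use in the chest cavity have been reported and include pain, hypotension and difficulty in removing the sponge", and that "there is an unquantifiable risk of injury to intrathoracic organs". It adds that removing black foam may injure underlying structures. H.2 item 5 bars reapplication after a foam-count discrepancy "until the surgeon confirms that no foam piece has been retained in the wound". E.1.2.3 item 3 makes organ injury a reason to remove the device.

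**The concern.** One classification drives three things: the safety rate, the urgent report and the hold. If it is ambiguous, two investigators could handle the same event differently, and a descriptive rate in 10 patients could not show that this had happened.

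The ambiguity falls on harms tied to the device under test. Retained foam and hypotension appear by name in neither H.1.1 nor H.1.2, and organ injury as such is absent from both. An event of this kind that is not classified as severe could be recorded locally without reaching the DSMB before the next patient is enrolled.

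**Working it through.** The plan gives no expected event rate, safety threshold or sample-size calculation, so there is no figure to reproduce. The check is mainly a comparison of the texts.

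**Step 1. What makes an event severe?**
- H.1.1: a list headed as potential events and never called exhaustive. It nevertheless behaves like a rule set, with thresholds, an instruction to report every new fistula as an SAE, and explicit exclusions.
- H.2: monitoring and reporting refer back to the listed events, while the endpoint sentence points forward.
- H.3.1: the trigger is that the investigator considers the event severe. The 24-hour clock starts when the event is recognised or classified as severe, so an event never so classified does not start it. H.3.4 instead counts from occurrence.
- H.3.3: CTCAE v4.0, with no grade named as the cut-off.

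These are different rules, and nothing says which one governs.

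**Step 2. What makes an event an adverse event at all?** The defining sentence of H.3.2 requires it to be unexpected. The next sentence is wider and admits signs or conditions that are unexpected *or* abnormal. The two do not agree. E.1.2.3 item 3 gives organ injury as an example of an unpredicted event, whereas H.1 predicts it.

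**Step 3. Foreseen harms against the lists.**

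| Harm | Foreseen in | Named in H.1.1 or H.1.2 | Indirect capture in H.1.1 |
|---|---|---|---|
| Retained foam | H.2 item 5 | No | Only through a listed consequence, such as worsening infection; treatment of pathogens from the initial culture does not count as a new infection |
| Organ injury from dressing or removal | H.1, E.1.2.3 | No | Partly: hemorrhage, massive hemoptysis, new fistula, ventilation, major arrhythmia, death |
| Hypotension | H.1; low systolic pressure is watched for in H.2 | No | Only as instability from hemorrhage or arrhythmia |

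The hemorrhage item reads "Intra-parenchymal/intrapleural hemorrhage leading to hemodynamic instability or requiring any intervention to specifically address the bleeding". An injury without such bleeding needs another listed consequence to qualify.

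**Step 4. Scale.** The denominator is taken from D.1: "A total of 10 patients will be enrolled in the intervention (V-AD) arm of the study". The plan does not say whether the rate counts patients or events; patients with at least one event are assumed here.
- Change per patient: 1/10 = 10 percentage points.
- Exact (Clopper-Pearson) 95% interval for 0/10: upper limit 1 − 0.025^(1/10) = 30.8%, so 0% to 30.8%.
- For 1/10: lower limit 1 − 0.975^(1/10) = 0.3%. The upper limit solves (1−p)^10 + 10p(1−p)^9 = 0.025, giving 44.5%.

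How likely such a case is depends on a probability the documents do not give. If each patient had probability p of an unlisted harm, the chance of at least one affected patient among 10 is 1 − (1−p)^10. That is 40% for p = 5%, 65% for p = 10% and 89% for p = 20%. These values of p are assumptions.

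**The case against.** A reader might infer that H.1.1 is the closed definition of a severe event, so that a retained sponge needing re-operation would certainly be reported as 0/10 with no report and no hold. The documents do not support that. The list is headed as potential, the endpoint sentence points to H.3, and H.3.1 requires all observed adverse events to be documented and reported. An investigator may call an unlisted event severe, and CTCAE grading may support that.

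A reader might also infer that the endpoint mostly counts complications of empyema and surgery. That too goes beyond the text. H.1 gives fistula, air leak, hemorrhage and death as possible results of device injury, and several of these are in H.1.1.

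The restriction to unexpected events is not applied consistently either: H.1 foresees pain, yet H.1.2 lists it as an adverse event. Other safeguards exist. Intermediate and minor complications are recorded, ease of dressing change is logged, blood pressure is monitored in hospital, and a foam discrepancy brings the surgeon to the wound.

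All of this stands, and it limits the conclusion to harms that *may* escape. It does not supply a definition. Local recording triggers neither DSMB report nor hold, judgement without a criterion is not a reproducible endpoint, and inconsistent use of the word in H.3.2 is itself a reason to correct it.

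**Conclusion.** The point holds in a limited form. Severe adverse event has no single operational definition, and the rules that stand in for one conflict. Under a literal reading, retained foam, dressing-related organ injury and hypotension may be left out of the severe-event rate, the 24-hour report and the hold. Judgement, grading or a listed consequence may still capture some of them.

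One misclassified patient would change the reported rate by 10 percentage points, from 1/10 to 0/10. The intervals overlap widely and the analysis is descriptive, so this is for scale only. The larger consequence is for oversight, because the DSMB acts on what is classified as severe. The conclusion rests on the wording of E.1.2.3, H.1, H.2 and H.3 and on a per-patient rate with 10 patients. It assumes nothing about how often these harms occur.

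**What to change.** 1. In H.3.2, replace the term for an unexpected medical event with *untoward medical event, whether or not expected*, and align the sentence that follows.
2. Name retained foam, organ injury related to the dressing or its removal, and hypotension in H.1.1 or H.1.2. The category and thresholds are for the sponsor and DSMB to set, since every SAE holds the study.
3. State one definition: a severe adverse event is any event in H.1.1, or any other event at or above a stated CTCAE grade. Make the endpoint sentence and the monitoring sentence in H.2 both refer to it. Pointing the endpoint to H.1.1 alone would close the list and lose the route through grading and judgement.
4. Reconcile E.1.2.3, H.1, H.1.1, H.1.2 and H.3 with that definition.

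The cost is protocol wording, a few form fields and possibly some additional DSMB reviews and holds. Their number cannot be estimated from the documents.

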After discharge, the patient will return to the outpatient clinic for wound inspection and dressing change by the surgeon once every two weeks and earlier, if necessary. During hospitalization and clinic visits, a Mayo Clinic photographer or a provider authorized to use the Mayo Clinic imaging software will photograph the wound, which will be a part of the permanent medical record of the patient. At every dressing change in and outside the hospital, the number of individual pieces of foam sponges will be entered in a logbook and accounted for during removal at the next change.

Figure 1: Algorithm for Patient Selection and Enrollment

E.1.2.2. Monitoring:

A prospective database of all patients in the study will be maintained and will record the following:

- a. Name, Medical Record number and Dates of dressing changes
- b. Pain scores visual analogue scores,
- c. Ease of dressing changes (Easy, moderately difficult, very difficult)
- d. Wound bed characteristics including amount of granulation tissue (minimal, moderate and significant) and dimensions (length x breadth x depth in centimeters).
- e. Duration of treatment
- f. Adverse events

E.1.2.3. Discontinuation of V-AD therapy:

1. In the absence of a noticeable improvement in the wound bed after 2 weeks of continuous V-AD therapy, the treatment plan will be re-assessed and the determination will be made as to whether the V-AD therapy should be discontinued.

2. The V-AD will be discontinued if the patient develops severe uncontrolled pain that does not respond to pain medications or a reduction in the negative pressure to -50 mm Hg.

3. In the event of any unpredicted adverse event, such as bleeding, injury to underlying organs, new onset of respiratory distress or allergy to the dressings will result in removing the V-AD.

4. Patients who require treatment with anticoagulation or antiplatelet agents after V-AD application will be removed from the study to avoid hemorrhagic complications.

F. DRUGS/ SUBSTANCES/ DEVICES

The V.A.C. Therapy System has many components that work together to apply negative pressure to wounds. The components include:

- 1. a porous foam dressing which comes in contact with the wound base and equally distributes negative pressure throughout the wound,
- 2. an airtight transparent adhesive drape that covers the foam dressing and
- 3. a software-controlled V.A.C Canister that is connected to the dressing by means of a transparent plastic tubing.

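### The first sentence of H.3.2 limits adverse events to unexpected ones, which leaves the status of harms foreseen in H.1 but not listed in H.1.1 or H.1.2 unclear

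*Combined protocol and SAP*

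**What the plan says.** All references are to the combined protocol and SAP.

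- **H.3.2, first sentence:** "An adverse event will be defined as any unexpected medical event associated with the use of the procedure in a human subject". The sentence goes on to set aside the question of whether the event is procedure-related. It does not do the same for expectedness.
- **H.3.2, second sentence:** "An adverse event can be any unexpected or abnormal clinical sign or condition temporally associated with the procedure".
- **H.1:** "The specific risks of V-AD use in the chest cavity have been reported and include pain, hypotension and difficulty in removing the sponge". It adds suction injury to skin and organ injury as general risks from use elsewhere in the body, and extends organ injury to the chest as a risk that cannot be quantified.
- **H.1.1**, headed "Potential Severe Adverse Events", and **H.1.2** list events without any expectedness test. H.1.1 includes "All new onset bronchopleural fistulas will be reported as SAE's". H.1.2 includes "Mild (<4/10, not requiring IV medication) to moderate pain (requiring IV medication or rated as >5/10".
- **H.2:** "We plan to monitor and report all of the above adverse events from the first application of the V-AD". H.2 also says that intermediate and minor complications are recorded, and defines safety by the rate of severe adverse events.
- **H.3.1 and H.3.3:** the principal investigator documents and reports all adverse events. Severe ones go to the DSMB within 24 hours and put the study on hold. Grading follows CTCAE version 4.0.
- **E.1.2.3 item 3** begins "In the event of any unpredicted adverse event, such as bleeding, injury to underlying organs".

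**The concern.** H.3.2 is the only formal definition of an adverse event in the plan, and the duties in H.3 to document, grade and report are all stated for adverse events. Expectedness normally governs how an event is reported, not whether it happened. A definition that starts from unexpected events can therefore exclude the harms that the investigators already associate with the device.

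The protocol calls safety a critical component and measures it by the severe-event rate. An event has to be an adverse event before it can be graded severe. If the definition is uncertain for some device-related harms, so is their route to the DSMB and into that rate.

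**Working it through.** The plan gives no figure to reproduce, so the check is a comparison of passages.

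**Step 1. Is H.3.2 consistent with itself?** The first sentence says what an adverse event will be, and the test is unexpected. The second says what an adverse event can be, and the test is unexpected or abnormal. A foreseen but abnormal finding passes the second and fails the first. Nothing says which sentence governs.

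**Step 2. Is H.3.2 consistent with the lists?** Pain is the clearest case. H.1 gives it as a reported risk of V-AD in the chest, H.1.2 lists it as an adverse event, and read literally it fails the first sentence of H.3.2.

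**Step 3. Which events does the conflict affect?**

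| Harm | How H.1 treats it | Named in H.1.1 or H.1.2? | First sentence of H.3.2 | Second sentence of H.3.2 |
|---|---|---|---|---|
| Pain | Reported chest risk | Yes, H.1.2 | Not met if read literally | Met as abnormal |
| Hypotension | Reported chest risk | Not as such; haemodynamic effect appears only as a qualifier of bleeding or arrhythmia | Not met if read literally | Met as abnormal |
| Difficult sponge removal | Reported chest risk | No | Not met if read literally | Arguable, since it may not be a clinical sign or condition |
| Suction injury to skin | General risk at other body sites | No | Arguable | Met as abnormal |
| Organ injury without major bleeding | Extrapolated, unquantified | Not as such, unless it appears as a listed event such as minor haemorrhage or a new fistula | Arguable | Met as abnormal |

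For pain the conflict has no effect on reporting, because H.2 covers every listed event. For the other four rows there is no list entry to settle the matter, and the answer depends on the sentence chosen.

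**Step 4. Can an unlisted event reach the severe-event rate?** Yes, in principle. H.3.1 speaks of adverse events considered severe and H.3.3 grades by CTCAE. Neither confines severity to the H.1.1 list. The unlisted event must first qualify as an adverse event under H.3.2.

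**Step 5. Scale.** D.1 sets the V-AD arm at 10 patients. If k patients are classed differently, a per-patient rate moves by k/10. For k = 1 this is 1/10 = 10 percentage points. The documents give no incidence for the four unlisted harms, so k is unknown. As an assumption for scale only, k = 1 to 3 gives 10 to 30 points on the overall adverse-event rate. The severe-event rate would move only for those patients whose event was also graded severe.

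**The case against.** The strongest reply is that the protocol captures these harms in other ways.

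- H.2 reports every listed event and records all lesser complications, with no expectedness test.
- E.1.2.2 makes pain scores and ease of dressing changes database fields, and H.2 monitors systolic pressure below 90 during admission.
- The words 'or abnormal' in H.3.2 can take in foreseen complications.
- H.1.1 is headed as potential events, not expected ones. H.1 raises bleeding and organ injury in the chest only by extrapolation or hypothesis, so they could still be unexpected when they occur.

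Most of this stands. It shows that the data are largely collected and that listed events are safe. It does not settle whether a foreseen, unlisted harm carries the adverse-event label, and grading and DSMB reporting depend on that label. Nor is a literal reading far-fetched: H.1.1 itself excludes sharp debridement from adverse events because it is normal in this setting.

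Three stronger inferences might tempt a reader, and the documents do not support them.

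- **That a literal H.3.2 would bring the count of anticipated complications to zero.** This requires ignoring the second sentence of H.3.2, the lists and the H.2 commitment.
- **That the two campuses would count differently.** H.3.1 and H.3.4 place identification and grading with the principal investigator, and nothing shows two definitions in use.
- **That E.1.2.3 item 3 alters event counts.** It governs removal of the device, and its examples name bleeding and organ injury, so it covers them despite the word 'unpredicted'.

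**Conclusion.** The inconsistency is real but narrow. The first sentence of H.3.2 conflicts with the second and with the listed events, most plainly pain. Reporting of listed events is protected by H.2. What remains open is the adverse-event status of harms that H.1 foresees and the lists do not name as such: hypotension, difficult sponge removal, skin suction injury, and organ injury without major bleeding. The case is firmest for the first two, which H.1 gives as already reported in the chest.

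The documents do not show that the severe-event rate would change, or by how much. The only size that follows from them is 10 percentage points per patient classed differently among 10. The conclusion assumes that someone might apply the first sentence as written, which the text permits but does not require. This is a wording inconsistency that should be corrected because the harms affected are those of the device under study.

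**What to change.** - In the first sentence of H.3.2, replace 'any unexpected medical event' with 'any unfavourable medical event, whether or not expected', and make the second sentence match.
- State that the events in H.1.1 and H.1.2 always count as adverse events, keeping the exceptions already written into H.1.1.
- Reconcile the word 'unpredicted' in E.1.2.3 item 3 with H.1, as a matter of wording only. No clinical rule is proposed.
- Optionally, record expectedness as a separate yes/no field, so that it can inform reporting without deciding what counts.

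The cost is a short amendment, plus one database field if the option is taken. It adds no patients, visits or procedures. The reported adverse-event rate may be slightly higher.
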